6.8.2 Percent predicted PFTs

The percent predicted PFT value, for each subject, is defined as (absolute PFT value / predicted PFT value) * 100.

The change from baseline in percent predicted PFT value is defined as (post-baseline percent predicted PFT value - baseline percent predicted PFT value).

For non by-visit summaries, visits defined by visit-windows will not be used. All available data from scheduled and unscheduled visits will be considered.

6.8.3 Data summaries

Summaries on the SAF set by treatment group include:

- Summary statistics and changes from baseline in percent predicted values of PFT parameters by visit
- Number (%) of subjects who had PFT measurements below 80% of predicted by visit
- Shift tables from baseline to lowest post-baseline presenting the frequency of subjects with normal and abnormal (categories are specified in the shell)
- Frequency (%) distribution of relevant pulmonary function test changes (<60% or <80% for any visit or 2 consecutive visits) for percent predicted FEV₁, FVC, and D_LCO

Summaries on the follow-up set include:

- Number (%) of subjects who had PFT measurements below 80% of predicted by time-window (days 1 to 45 after study drug discontinuation and more than 45 days after study drug discontinuation)

The following plots will be provided on the SAF set:

- Box and whisker plot for PFT parameters (percent predicted values) by visit

6.9 Ophthalmic evaluations

The ophthalmic evaluation includes assessment of visual acuity, assessment of optical coherence tomography (OCT), [REDACTED] and assessment of macular edema.

For the assessment of visual acuity, if the decimal score is not available but the Corrected Snellen equivalent is available, the decimal score will be calculated by division (e.g., Corrected Snellen equivalent = 10/20 infers that decimal score = 0.5). All decimal scores will be converted to the LogMAR (log of the minimum angle of resolution) equivalent by taking the negative of the common logarithm (i.e., $-\log_{10}$ (decimal acuity score)) (Holladay 1997). Summaries of the visual acuity will be performed on the converted scores (i.e., LogMAR equivalent).

The central foveal thickness (CFT) and macular volume from OCT will be summarized by visit where nominal visits are used as they are. Other ophthalmic data will be summarized by visit where visits are defined by the visit-windows. Last assessment on study drug and unscheduled assessment may also be summarized as specified in the table shells. If multiple unscheduled values exist for a subject, the worst (i.e., highest) value will be used in the CFT and macular volume summaries and the largest (positive) percent change from baseline value will be used in the CFT and macular volume summaries. For the CFT summaries on the FUS, the same rules apply when multiple observations exist for a subject in a predefined follow-up visit-window.

If two or more visual acuity values for the same eye of a subject are available at a post-baseline visit-window, the worst of all values will be used in the summaries. The same rules apply for the Sloan letter chart testing data summaries. Note that the worst value for visual acuity refers to the smallest value in the decimal score (or equivalently refers to the largest value in the logMAR scale). The worst value for the other parameters in the Sloan letter chart testing (i.e., 100% chart total correct and 2.5% chart total correct) refers to the smallest value.

Visual acuity and change from baseline will be categorized by pre-defined intervals. CFT and percent change from baseline will also be categorized by pre-defined intervals. Details will be specified in the table shell document (RAP Module 7.1).

6.9.1 Data summaries

Summaries on the SAF set by treatment group include:

- Summary statistics of visual acuity and changes from baseline by visit
- Summary statistics of CFT and percent changes from baseline by visit
- Frequency (%) distribution of categorized visual acuity and change from baseline by visit
- Frequency (%) distribution of categorized CFT percent change from baseline by visit
- Summary of diagnosis of macular edema
- Summary statistics of macular volume and percent change from baseline by visit
- Summary statistics of Sloan letter chart testing data and changes from baseline by chart type and visit.

6.10 Chest x-ray and MRI of chest

Chest x-ray was originally scheduled for screening and Month 24 visits but was removed according to protocol Amendment 3. A listing of the chest x-ray (or chest MRI) data will be provided.

6.11 Skin assessment

A complete skin examination will be performed at screening and EOT. Results of the skin exams are categorical (normal or abnormal with abnormal types) and will be summarized by treatment group.

6.12 C-SSRS

The C-SSRS questionnaire will be administered electronically (eC-SSRS), via an interactive voice response (IVR) system. However, as per internal Novartis guidelines, a CRF page 'Supplemental Data for Suicidal Ideation and Behavior Categories' is also used for those cases when the subject did not conduct the phone interview because, e.g. the phone system was inoperable, the subject was hospitalized and unable to conduct the interview, or the subject refused to conduct the interview/withdrew from the study and external information on suicidal ideation and behavior is required. For these cases the information will be entered on the supplemental suicide CRF page by the patient or caregiver as appropriate. In addition, cases may require additional information or additional information may be available. The information will be collected from external parties (spouse, caregiver, nurse, investigator, etc.) through means of the supplemental suicide CRF page.

In the analysis, data from both sources (IVR eC-SSRS and Supplemental CRF) will be used in a pooled manner and no distinction will be made between the two. There are cases when incomplete call was made via IVR and any data from incomplete call will not be included in analysis. When data from both sources are available on the same date, both data will be analyzed.

The Columbia Suicide Severity Rating Scale (C-SSRS) data will be mapped to Columbia Classification Algorithm for Suicide assessment (C-CASA) as per FDA guidance on suicidality. Following is a mapping algorithm (code and category) that should be applied for the C-SSRS:

Table 6-5 Mapping between C-CASA and C-SSRS scales for suicidal ideation and behavior

Event code	C-CASA event	C-SSRS event
1	Suicide completed	Suicide completed
2	Suicide attempt	Actual attempt
3	Preparatory Actions Toward Imminent Suicidal Behavior	Interrupted attempt Aborted attempt Preparatory acts or behavior
4	Suicidal Ideation	Subscale code and event 1. Wish to be dead 2. Active suicidal thoughts (non-specific) 3. Active suicidal thoughts with method (no plan) 4. Active suicidal thoughts with intent (no plan) 5. Active suicidal thoughts with plan and intent
7	Self-Injurious Behavior Without Suicidal Intent	Self-injurious behavior, no suicidal intent

C-SSRS data used here are “yes” or “no”.

Source: [\[Gassmann-Mayer et al \(2011\)\]](#)

The proportion of subjects with completed suicide, suicide attempt, preparatory actions toward imminent suicidal behavior, suicidal ideation, and self-injurious behavior without suicidal intent as per the C-CASA scale during the study will be summarized by treatment group.

The following variables will also be summarized:

1. The proportion of subjects with any suicidal behavior engaged in during the study (answered “yes” for any of the C-SSRS suicidal behaviors during the study)
2. The proportion of subjects with suicidality (answered “yes” for any of the C-SSRS suicidal behaviors during the study and/or answered “yes” for any of the C-SSRS ideation during the study)

Similar summary will also be provided for baseline.

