3.8.6 Multiple assessments within visit windows

For visit windows defined in [Sections 3.8.4.2](#) and [3.8.5](#), multiple records may exist in one particular visit window. All results (scheduled and unscheduled) will be displayed in listings, but only one value (observed or derived) “representing” the subject will be selected for summary statistics by visit-window. The following rules (unless otherwise specified) will be applied to obtain one value per subject per visit-window which will be used in the by-visit summaries.

- For quantitative variables (i.e., continuous variables for which summary statistics and change from baseline tables will be provided), the average of the multiple records will be used.
- For qualitative variables (i.e., binary or nominal variables for which incidence rates and frequency distribution tables will be provided), the worst record (from scheduled and unscheduled visits) will be used. It is noted that in the analyses performed, worst case is always well defined.

Note that “Last assessment on study drug” is not like other visit-windows where multiple assessments could occur. The assessment to be summarized at that time point is the last on drug observation which is the last observation a subject has while he or she is on study drug. Therefore, the above multiple assessment rules do not apply.

In addition, the multiple assessment rules do not apply to the first dose/second dose/dose increase/restart dose monitoring data.

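### SAP 6.12 discards every answer from an incomplete IVR call, so a subject whose only C-SSRS 'yes' came in such a call is not counted in the C-SSRS and C-CASA summaries

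*SAP*

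**What the plan says.** SAP 6.12 names two sources of C-SSRS data. The main one is the interview by interactive voice response (IVR). The second is a supplemental CRF page, which "is also used for those cases when the subject did not conduct the phone interview" and may also hold further information obtained from people such as a caregiver, nurse or investigator. In the analysis, "data from both sources (IVR eC-SSRS and Supplemental CRF) will be used in a pooled manner".

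The same paragraph then notes that some IVR calls were not completed and sets the rule at issue: "any data from incomplete call will not be included in analysis". In the published text it does not define an incomplete call, separate positive from negative answers, or require a repeat call or a supplemental entry. It adds: "When data from both sources are available on the same date, both data will be analyzed".

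The summaries in SAP 6.12 and 6.12.1 are proportions of subjects over the whole study. One is described as "The proportion of subjects with any suicidal behavior engaged in during the study", where a subject qualifies by having "answered “yes” for any of the C-SSRS suicidal behaviors during the study". A second adds ideation to behaviour, and the C-CASA categories are summarised as well. A similar baseline summary is planned. Protocol 9.5.3 commits to summarising treatment-emergent ideation and behaviour and mentions no exclusion for incomplete calls.

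**The concern.** An incomplete interview makes a run of 'no' answers inconclusive, because a later item might have been answered 'yes'. It does not make a 'yes' inconclusive. For a variable defined as any 'yes', one positive answer settles the subject's status and no unanswered item can reverse it. The rule treats the two situations alike and removes both.

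At stake is the count of subjects with suicidal ideation or behaviour in a paediatric trial with about 95 subjects per arm. A few subjects are a visible share of such an arm, and a reader of the C-SSRS table would not know that a recorded positive answer had been set aside.

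**Working it through.** There is no figure in the plan to reproduce, so the main check is of the text, followed by a calculation of scale.

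**1. What the rule does to a subject's status.** For one category (for example, any suicidal behaviour), let the subject be positive if at least one analysed record contains a 'yes'.

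| Subject's records in that category | Status on all recorded answers | Status under SAP 6.12 |
|---|---|---|
| 'Yes' in a completed call or on the supplemental page, with or without a 'yes' in an incomplete call | Positive | Positive |
| Only 'yes' is in an incomplete call | Positive | Not counted as positive |
| Only 'no' answers, some in an incomplete call | Partly unknown | Not counted as positive |

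Only the second row is misclassified against the recorded data. In that row the subject moves from positive to not positive, so the during-study numerator can fall but cannot rise.

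**2. Whether the text restores the lost answer.**
- *Supplemental CRF page (SAP 6.12).* It may be used when more information is needed or available. An unfinished call is not named as a trigger.
- *Same-date rule (SAP 6.12).* Analysing both sources on one date does not bring back IVR data already excluded.
- *Adverse events (Protocol 6.5.8).* Investigators review system reports on the visit day, and adverse events found through the C-SSRS are documented. Such a case can reach the AE tables but not the C-SSRS or C-CASA proportions. The protocol does not say whether the reports cover unfinished calls.
- *Listings (SAP 6).* There is a general commitment to list safety data. It does not mention incomplete calls.
- *Later completed call.* It helps only if the subject answers 'yes' again in the same category.

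Each route is possible; none is required.

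**3. Baseline.** The exclusion is not limited to post-baseline calls. If a 'yes' in an incomplete baseline call is discarded and the subject later answers 'yes', the later answer could be classed as treatment-emergent when it is not. Here the error runs upward.

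**4. Scale.** Planned size is 95 per arm (Protocol 9.6, SAP 9.1). One subject losing the only positive record changes the arm's proportion by 1/95 = 0.0105, or 1.05 percentage points, with the subject kept in the denominator.

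The documents give neither the frequency of a 'yes' nor that of incomplete calls, so the following inputs are assumptions. Let p be the proportion of subjects ever positive and f the share of those whose only 'yes' lies in an incomplete call. With independent subjects, the chance that an arm loses at least one positive subject is 1 − (1 − p·f)^95.

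| p | f | Expected positives, true | Expected positives, reported | Chance of losing at least one |
|---|---|---|---|---|
| 2% | 5% | 1.90 | 1.80 | 9% |
| 5% | 10% | 4.75 | 4.28 | 38% |
| 10% | 50% | 9.50 | 4.75 | 99% |

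For the middle row: p·f = 0.005 and 1 − 0.995^95 = 0.379. A range from 9% to 99% shows that the effect depends almost wholly on figures the documents do not give.

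**The case against.** The best defence is that the gap is narrow. It concerns descriptive proportions for which SAP 6.12 plans no test. The questionnaire is repeated at scheduled and unscheduled visits, so a subject has other chances to be counted. A broken-off call with a worrying answer fits the supplemental page's wording on additional information, and same-day review by the investigator is unaffected. An unfinished call may also contain mis-keyed answers. All of this stands as a limit on size and scope, but none of it obliges anyone to carry the 'yes' into the C-SSRS tables.

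Several stronger readings are tempting and should not be drawn:
- *The event vanishes from the safety analysis.* The rule governs the C-SSRS analysis. AE tables and listings may still show the event.
- *Every lost 'yes' costs 1.05 percentage points.* The variable is per subject, so this holds only when the subject has no other positive record in that category.
- *The SAP contradicts itself.* SAP 3.8.6 says that for qualitative data "the worst record (from scheduled and unscheduled visits) will be used", but this chooses among records within visit windows and yields where another rule is specified. The tension is one of principle. SAP 6.5.2 is the closer parallel: there a single qualifying laboratory result makes the subject notable.
- *The rule hides a difference between arms, or distressed adolescents are the ones who hang up.* The rule is the same for both arms, and the documents give no reasons for incomplete calls and no frequency by arm.

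**Conclusion.** The point holds for the C-SSRS and C-CASA summaries. Followed as written, SAP 6.12 leaves out any subject whose only 'yes' in a category was recorded in an incomplete call, and no provision ensures that the event is recovered there.

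For during-study counts the error is one-directional, towards fewer events. A reader might infer that the rule can never overstate anything. That fails for the treatment-emergent status promised in Protocol 9.5.3, where a lost baseline 'yes' could make later ideation look new.

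The size is 1.05 percentage points of an arm of 95 for each subject who loses the only positive record. How many such subjects there are cannot be estimated from the documents. If every incomplete call was repeated in full with the same answers, the results would not change. The primary and key secondary efficacy analyses are untouched, as is the handling of individual patients.

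**What to change.** In SAP 6.12, replace the exclusion with a rule at the level of the item:
- include answered items from incomplete calls, at baseline and after it;
- count any recorded 'yes' as positive and treat only unanswered items as missing;
- define what makes a call incomplete;
- report by arm the number of incomplete calls and the number of positive answers in them;
- repeat the summaries without incomplete calls as a sensitivity table.

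The cost is a short change of wording, one programming change and one extra table. Subjects whose only partial-call data are 'no' need a missing-data flag, since their status is not established. A few mis-keyed answers may enter; the sensitivity table would show how much depends on them.

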 - ALT, AST, alkaline phosphatase, GGT, >2 x upper limit of normal (ULN) range for age (for pre-pubertal patients > 1 X ULN or > 2 X ULN if currently treated with IFN or glatiramer acetate). Elevations of alkaline phosphatase should not be used in isolation to exclude subjects, and would require Investigator discretion.
 - Bilirubin elevations not in the context of Gilberts Syndrome: Total and conjugated bilirubin >1.5 X ULN (for pre-pubertal patients >1 X ULN or > 1.5 X ULN if currently treated with IFN or glatiramer acetate).
 16. Patients with severe renal insufficiency (GFR <30 ml/min/1.73 m²).
 17. Patients with lymphocyte count < 800 cells (mm³).
 18. Patients with any of the following neurologic/psychiatric disorder:
 - History of any type of epileptic seizure(s) as well as psychogenic non-epileptic seizure(s) during the past 12 months before screening;
 - History of substance abuse (drug or alcohol) or any other factor (i.e., serious psychiatric condition) that may interfere with the subject's ability to cooperate and comply with the study procedures;
 - Progressive neurological disorder, other than MS, which may affect participation in the study or require the use of medications not allowed by the protocol
 19. Patients unable to undergo MRI scans, including claustrophobia or history of hypersensitivity to gadolinium-DTPA.
 20. Pregnant or nursing females, where pregnancy is defined as the state of a female after conception and until the termination of gestation, confirmed by a positive HCG laboratory test.

21. Female patients of childbearing potential, defined as all females physiologically capable of becoming pregnant, unless they agree to abstinence or, if sexually active, the use of contraception as defined in [Section 6.6](#).
22. History of hypersensitivity to any of the study drugs or to drugs of similar chemical classes.
23. Patients with a score of “yes” on item 4 or 5 of the Suicidal Ideation section of the C-SSRS, if this ideation occurred in the past 6 months, or with a score of “yes” on any item of the Suicidal Behavior section, except for “Non-Suicidal Self Injurious Behavior”, if this behavior occurred in the past 2 years.
24. Patients who have received an investigational drug or therapy within 180 days or 5 half-lives of randomization, whichever is longer.

No additional exclusions may be applied by the investigator, in order to ensure that the study population will be representative of all eligible patients.

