Pulmonary function test (PFT) data will consist of the following parameters: FEV₁, FVC, and DLCO. Summary tables and listings will be produced for percentage of predicted value when applicable. For the purpose of the statistical analysis the percentage of predicted value will be calculated centrally and this centrally calculated value will be used for the study level analysis. The data will be summarized by presenting summary statistics of change from baseline. The frequency of patients who had PFT measurements below 80% of predicted, and shift tables presenting the frequency of patients with normal ($\geq 80\%$ of predicted when applicable) and abnormal ($< 80\%$ of predicted when applicable) will be presented.

The ophthalmic data will be summarized using the distribution tables, summary statistics, and change from baseline by visit and treatment group for visual acuity, OCT, and other ophthalmic parameters. The patient listing with these parameters will also be provided.

ECG intervals will be summarized by presenting summary statistics for change from baseline values by visit. The (uncorrected) QT interval will be corrected according to the Bazett's and Fridericia formulae. Maximum increase in corrected QT interval from baseline will be used to summarize the frequencies of patients who fulfill the abnormality criteria based on the corrected QT interval will be calculated.

Frequency distribution of treatment-emergent suicidal ideation and behaviors from C-SSRS will be summarized. The proportion of patients who have completed suicide, suicide attempt, and preparatory actions toward imminent suicidal behavior, suicidal ideation, and self-injurious behavior without suicidal intent will be summarized by treatment group.

Safety data will be summarized for the overall population and listings provided for the pre-pubertal subgroup.

Follow-up data will be summarized to assess patients' safety after discontinuation of the study drug.

Fingolimod Extension Phase:

All safety endpoints, including adverse events (adjusted by the duration of fingolimod exposure), bradycardia events, laboratory tests, vital signs, pulmonary function tests, ophthalmic examinations, C-SSRS, ECG data, and [REDACTED] will also be summarized based on the long-term safety data during fingolimod treatment, by core treatment and combined using the Fingolimod Treated Safety Set. [REDACTED]

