3.8.2 Baseline

In general, a baseline value refers to the last measurement made prior to the administration of the first dose of the study drug. Assessments made on Day 1 may occur before or after the first dose. The following rules will be applied to determine which record is the last measurement prior to the first dose (i.e., the baseline value).

- Consider all records with an assessment date before the first dose date or with an assessment date on the same day of the first dose date and from Day 1 visit or before (i.e., visit\repeat visit number < 3). Baseline is the last record after sorting all above records with respect to assessment date, visit and repeat visit number.
- Some data specific rules for determining baseline will be applied as described below or in data specific sections if applicable.

For vital signs, the mean of the Day 1 pre-dose value will be used as baseline. If unavailable, the last available (including unscheduled) value before the first dose will be used.

For ECG, the Day 1 pre-dose value will be used as baseline. If unavailable, the last available (including unscheduled) value before the first dose will be used.

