5.2 Population pharmacokinetic/pharmacodynamics analysis

Population PK/PD modeling approaches will be used to relate the individual fingolimod PK parameter estimates to key efficacy measurements (MRI-related, relapse-related). A modeling plan will be prepared before final clinical database lock providing details for the proposed PK/PD analysis. This modeling plan will be prepared and executed by PMX group. The report analysis plan and the results will be provided separately.

6 Safety evaluation

Safety assessments include adverse events, bradycardia (first dose) events, laboratory tests, vital signs, ECG, pulmonary function tests, ophthalmic examinations, Tanner stages (bone x-ray), skin assessments, and C-SSRS data.

All safety data will be summarized on the SAF set. Some safety data (AEs, vital signs, labs, PFTs and C-SSRS) will also be summarized on the follow-up set by time-window (days 1 to 45 after study drug discontinuation and more than 45 days after study drug discontinuation) to assess subjects' safety after discontinuation of the study drug.

Unless otherwise specified, safety assessments in core phase (core phase data defined in section 3.8.3) more than 45 days after the study drug discontinuation will not be included in the summaries on the safety set but will be considered in the summaries on the follow-up set.

Adverse events starting before the first dose date will be excluded from the adverse event.

Details of the safety data summaries will be provided in the sections below. All safety data will also be presented in the listings.

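### The protocol's treatment-emergent C-SSRS summary has no counterpart in the SAP, whose on-study counts cannot separate new or worsened cases from repeated baseline answers

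*SAP*

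**What the plan says.** Protocol 9.5.3 (Safety variables) contains two consecutive C-SSRS sentences.

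- The first: "Frequency distribution of treatment-emergent suicidal ideation and behaviors from C-SSRS will be summarized". The term treatment-emergent is not defined.
- The second: "The proportion of patients who have completed suicide, suicide attempt, and preparatory actions toward imminent suicidal behavior, suicidal ideation, and self-injurious behavior" (in full, self-injury without suicidal intent), by treatment group and with no treatment-emergent qualifier.

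SAP 6.12 carries over the second: "The proportion of subjects with completed suicide, suicide attempt, preparatory actions toward imminent suicidal behavior, suicidal ideation, and self-injurious behavior without suicidal intent", on the C-CASA scale, during the study, by treatment group. It adds two composites. One is any suicidal behaviour. The other is suicidality, defined as "answered “yes” for any of the C-SSRS suicidal behaviors during the study and/or answered “yes” for any of the C-SSRS ideation during the study". SAP 6.12.1 lists the same three summaries for the safety set and repeats them for the follow-up set.

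On baseline, SAP 6.12 says only "Similar summary will also be provided for baseline". The general rule in SAP 3.8.2 is that "a baseline value refers to the last measurement made prior to the administration of the first dose of the study drug".

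On entry, Protocol 4.2 exclusion 23 bars a 'yes' on item 4 or 5 "of the Suicidal Ideation section of the C-SSRS, if this ideation occurred in the past 6 months", and suicidal behaviour in the past 2 years. It expressly exempts non-suicidal self-injurious behaviour.

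**The concern.** A treatment-emergent summary exists to separate what appeared or got worse after the first dose from what the patient brought into the trial. The protocol promises one for a safety outcome in adolescents, and the SAP does not provide it. The table the SAP does provide mixes three groups: patients with a first report on study, patients whose earlier report became worse, and patients who repeat an unchanged answer. A reader of the report could not tell these apart in any planned summary table. The exclusion criterion leaves room for the third group, because ideation items 1-3 and non-suicidal self-injury are both permitted at entry and both are reported categories in SAP Table 6-5.

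**Working it through.** The documents state no C-SSRS figure, so there is nothing to reproduce. The check is a comparison of text, followed by an illustration of size.

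**1. Match the commitments to the tables.** The protocol's category proportions by arm are present in SAP 6.12 and 6.12.1. Its treatment-emergent distribution is not. Neither section uses the term, and neither has a rule that refers to the patient's own baseline.

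**2. Can the baseline table stand in for it?** No. It is a second marginal count. Suppose 4 of 95 patients in an arm are positive at baseline and 4 of 95 on study. Both tables show 4.2%, whether the on-study cases are the same four patients (none new) or four different ones (all new). Elsewhere the SAP does link each patient to baseline: shift tables for laboratory results (6.5.4) and pulmonary function (6.8.3), and QTc increases from baseline (6.6.2).

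**3. Is worsening visible?** Table 6-5 maps ideation items 1 to 5 to a single event code, 4. A patient at item 1 before treatment and item 5 on study is counted as ideation in both tables.

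**4. When does 'during the study' start?** SAP 3.8.5 gives an end for safety-set summaries: 45 days after the last dose. No start is given for the C-SSRS. Protocol 3.1 places the pre-randomization period inside the Core Phase, and SAP 3.8.3 sets no lower bound on core phase data. The one explicit pre-dose rule, in the opening of SAP section 6, covers adverse events only: "Adverse events starting before the first dose date will be excluded from the adverse event". The separate baseline summary suggests that on-study is meant to exclude pre-dose answers, but the SAP does not say so.

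**5. Illustration of size.** Let b be the proportion with permitted ideation at baseline, r the share of those who answer 'yes' again after the first dose, and q the new-onset proportion among the rest. All three are assumptions.

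- New onset = q(1 - b)
- Any 'yes' on study = q(1 - b) + r·b
- Excess = r·b, or 95·r·b patients in an arm of the planned 95

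With q = 3%:

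| b | New onset | Any 'yes', r = 0 | Any 'yes', r = 0.5 | Any 'yes', r = 1 | Excess patients per arm (r = 0 / 0.5 / 1) |
|---|---|---|---|---|---|
| 2% | 2.94% | 2.94% | 3.94% | 4.94% | 0 / 1.0 / 1.9 |
| 5% | 2.85% | 2.85% | 5.35% | 7.85% | 0 / 2.4 / 4.8 |
| 10% | 2.70% | 2.70% | 7.70% | 12.70% | 0 / 4.8 / 9.5 |

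**6. Effect on the comparison.** Take b = 5% and r = 0.5 in both arms, with q = 3% in one and 6% in the other.

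- New onset: 2.85% against 5.70%, difference 2.85 points, ratio 2.00.
- Any 'yes': 5.35% against 8.20%, difference 2.85 points, ratio 1.53.

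With equal b and r, the term r·b cancels from the difference, and only the ratio shrinks.

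**The case against.** The strongest reply has four parts.

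- **The SAP sentence is faithful to the protocol.** It implements the protocol's second commitment almost exactly. This stands. The defect is that the first commitment is missing, not that the existing table is wrong.
- **Treatment-emergent is undefined in the protocol** and could mean no more than occurring on treatment. On that reading the gap shrinks to the unstated start of the window. But the protocol lists the two summaries separately, and this reading makes the first largely redundant.
- **New or worse events have another route.** Protocol 7.1 defines adverse events as appearing or worsening after study drug starts, Protocol 6.5.8 requires adverse events found through the C-SSRS to be documented, and SAP section 6 lists all safety data by patient. This softens the harm, but it is not the promised summary.
- **A baseline imbalance would be seen.** The summary that the baseline table mirrors is by treatment group. Three extra repeating patients in one arm would add 3/95 = 3.2 points to the on-study figure, and the baseline table should show the imbalance beside it. So the documents do not support the inference that an imbalance would pass unseen as a drug signal.

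A reader might also infer that all ideation present at entry is reported as an on-study event. It is not. Ideation reported only before the first dose belongs in the baseline summary. It enters the on-study count if it is reported again, or if 'during the study' is read to include pre-dose assessments.

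**Conclusion.** The point holds as an omission. The SAP drops a safety summary that the protocol promises. Its remaining tables count an unchanged repeat of a baseline answer as an on-study case, and they hide worsening within ideation. The size cannot be determined from the documents. It is r·b per arm, which is zero if no baseline case repeats, and the figures above rest wholly on assumed b, r and q. The documents do not say that patients usually repeat the answer.

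Two further inferences should not be drawn. The first is that a true difference between arms is diluted. The absolute difference is unchanged when b and r are equal across arms, as randomization gives in expectation; only a ratio shrinks, and SAP 6.12 plans descriptive proportions with no ratio or test. The second is that suicidality is an established concern for either drug. Protocol 1.1 does not include it among fingolimod's safety areas of note, and the Amendment 2 rationale attributes the suicidality changes to the sponsor's own safety guidelines.

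This is a minor point. No primary or key secondary conclusion depends on it.

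**What to change.** In SAP 6.12, before database lock:

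1. State that 'during the study' means after the first dose and, for the safety set, within the 45-day cutoff in SAP 3.8.5.
2. Define treatment-emergent as an ideation category (items 1-5) worse than the patient's worst pre-dose category, or a behaviour not reported before the first dose. Worst pre-dose needs to be written out, because the default in SAP 3.8.2 takes the last record and could miss ideation reported only at an earlier assessment.
3. Add a by-arm table of treatment-emergent ideation and behaviour, or a shift table from worst pre-dose to worst post-baseline category, to SAP 6.12.1. Keep the existing any-'yes' and baseline summaries beside it.

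The cost is one derived flag and one table. No new data are needed.
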